14.6. Prior and Concomitant Medications and Nonpharmacologic Procedures

Each patient's prior and concomitant medication use will be coded using the World Health Organization Drug Dictionary, and the frequency and percentage of concomitant medications will be summarized. Medications will be summarized by Anatomic-Therapeutic-Chemical class and generic name using frequency counts and percentages of patients in the Safety set.

14.7. Treatment Compliance

The number of infusions received per patient will be tabulated for the FAS and Safety sets.

14.8. Efficacy Analyses

Efficacy analyses will be performed using the FAS. Continuous variables will be summarized using descriptive statistics, including number of observations and mean, SD, median, minimum, and maximum values. Categorical variables will be summarized by frequency counts and percentage of patients. Analyses will be conducted separately for naïve and previously eculizumab-treated patients.

14.9. Safety Analyses

14.9.1. Adverse Events

The following definitions will be used for AEs:

- Pretreatment adverse events: Any AE that starts after providing informed consent, but before the first infusion of study drug
- Treatment-emergent adverse event: Any AE that starts during or after the first infusion of study drug.
- Treatment-emergent SAE: A treatment-emergent AE (TEAE) that is serious (refer to Section 11.7.4 for definitions).

The incidence of TEAEs, TEAEs leading to withdrawal from the study, TEAEs leading to study treatment discontinuation, drug-related TEAEs, TEAEs during study drug administration, severe TEAEs, and SAEs will be summarized. All AEs will be coded using MedDRA version 18 or higher, and will be summarized by system organ class and PT. Detailed by-patient listings of TEAEs, SAEs, related TEAEs, TEAEs during study drug administration, TEAEs leading to withdrawal from the study, and TEAEs leading to study treatment discontinuation will be provided.

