11.7. Adverse Event Management

An AE is any untoward medical occurrence in a patient administered a pharmaceutical product and which does not necessarily have a causal relationship with this treatment. An AE can therefore be any unfavorable or unintended sign (eg, an abnormal laboratory finding), symptom, or disease temporally associated with the use of a medicinal product, whether or not considered related to the medicinal product.

Situations in which an untoward medical occurrence did not occur (eg, hospitalization for elective surgery if planned before the start of the study, admissions for social reasons or for convenience), and anticipated day-to-day fluctuations of pre-existing disease(s) or condition(s) present or detected at the start of the study that do not worsen are not AEs.

Transfusions are treated as efficacy endpoints (see Section 6.2). Transfusions administered in the inpatient or outpatient setting should not be captured as AEs or SAEs unless identified as such by the Investigator.

Lack of drug effect is not an AE in clinical studies, because the purpose of the clinical study is to establish drug effect.

A medication error (including intentional misuse, abuse, and overdose of the product) or use other than what is defined in the protocol is not considered an AE unless there is an untoward medical occurrence as a result of a medication error.

Cases of pregnancy that occur during maternal or paternal exposure to investigational product are to be reported within 24 hours of Investigator/site awareness. Data on fetal outcome and breastfeeding will be collected for regulatory reporting and safety evaluation.

Adverse events should be recorded from the time of signed consent. An AE reported after informed consent but before study drug administration will be considered a pretreatment AE.

Alexion has reporting standards for AEs that are to be followed as described in Section 11.7.6, regardless of applicable regulatory requirements that may be less stringent.

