11.7.2. Severity Assessment

The severity of AEs will be graded using Common Terminology Criteria for Adverse Events (CTCAE) version 4.03 or higher. A grading (severity) scale is provided for each AE term. Each CTCAE term is a Lowest Level Term (LLT) per the Medical Dictionary for Regulatory Activities (MedDRA®). Each LLT will be coded to a MedDRA preferred term (PT).

Grade refers to the severity of the AE. The CTCAE assigns a grade of 1 through 5, with unique clinical descriptions of severity for each AE (Table 7).

Table 7:	Adverse	Event Severity	Grading Scale
----------	---------	----------------	----------------------

Grade	Description
Grade 1	Mild; asymptomatic or mild symptoms; clinical or diagnostic observations only; intervention not indicated
Grade 2	Moderate; minimal, local or noninvasive intervention indicated; limiting age-appropriate instrumental ADL ^a
Grade 3	Severe or medically significant, but not immediately life-threatening; hospitalization or prolongation of hospitalization indicated; disabling; limiting self-care ADL ^b
Grade 4	Life-threatening consequences; urgent intervention indicated.
Grade 5	Death related to AE.

Abbreviations: ADL = activities of daily living; AE = adverse event

Any change in the severity of an AE should be documented based on specific guidelines in the eCRF Completion Guidelines.

Severity and seriousness must be differentiated: severity describes the intensity of an AE, while the term seriousness refers to an AE that has met specific criteria for an SAE as described in Section 11.7.4.

^a Instrumental ADL refers to preparing meals, shopping for groceries or clothes, using the telephone, managing money, etc.

^b Self-care ADL refers to bathing, dressing and undressing, feeding self, using the toilet, taking medications, and not bedridden.

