7.3.2. Adverse Events (AEs)

Adverse Events (AEs) will be classified by System Organ Class (SOC) and Preferred Term (PT) using the latest available version of MedDRA and will be reported by naïve, previously eculizumab-treated patients and total. The adverse events will be determined as occurring prior to treatment (pre-treatment) or as on or after first treatment (treatment-emergent) as described in Section 9.3. Analyses of Pre-Treatment Adverse Events (PTAEs) and Treatment-Emergent Adverse Events (TEAEs) will be tabulated and presented separately. Patients having multiple AEs within a category (e.g., overall, SOC, PT) will be counted once in that category. For severity/relationship tables, the patient's highest grade/most related event within a category will be counted. Percentages will be based on the number of treated patients in the Safety Set within naïve, previously eculizumab-treated patients and total. Tables will be sorted by descending frequency of SOC and by descending frequency of PT within SOC.

Listings will be provided for all TEAEs and PTAEs for the Safety Set.

Adverse events will include the displays described in the following sub-sections.

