All post baseline records including those that occurred outside the specified protocol windows will be assigned to an appropriate analysis visit by using the following scheme and will be included in the analysis of the specific assessment, where applicable.

Generally, the lower bound and the upper bound for each analysis visit window is defined as the midpoint of the target dates between 2 consecutive scheduled visits. The upper bound of the last visit window is set as the target date + 7 days. If the date of assessment falls in between the lower bound and the upper bound for a visit as defined in the protocol schedule of assessment, then it will be assigned to that visit. If the interval separating 2 scheduled visits is an even number of days, that middle day will be included in the lower bound of the next visit window.

For example, for an assessment with a scheduled visit on Day 127, and a prior scheduled visit on Day 99 and subsequent scheduled visit on Day 155, the window will start at 113 days from baseline and will go to 140 days from baseline.

If only 1 record is within an analysis visit window, the data from that record will be used in the analysis. If more than 1 record is within the same analysis visit window, the record closest to the midpoint of the interval will be used in the analysis. If 2 records are “tied” before and after the middle of the interval, the earlier record will be used in the analysis.

Please refer to the following table for visit window definitions.

Table 4: Visit Window

Endpoint	Visit	Nominal Day	Start (Day)	End (Day)
Chemistry/Hematology/ Vital Signs	Screening		-28	0
	Day 1	1	1	1
	Day 15	15	8	28
	Day 43	43	29	56
	Day 71	71	57	84
	Day 99	99	85	112
	Day 127	127	113	140
	Day 155	155	141	168
	Day 183	183	169	196
FACIT Fatigue/Urinalysis	Screening		-28	0
	Day 1	1	1	1
	Day 15	15	8	42
	Day 71	71	43	98
	Day 127	127	99	154
	Day 183	183	155	210
	PNH Clone	Screening		-28
	Day 1	1	1	1
	Day 71	71	36	126
	Day 183	183	127	266

Adverse Events

Treatment-emergent AEs (TEAEs) are events with start dates and start times on or after the date and time of the first ALXN1210 dose. If the start date of an AE is partially or completely missing and the end (stop) date and time of the AE does not indicate that it occurred prior to first dose, then the determination of treatment-emergent status will be based on the following:

- If the start year is after the year of the first study drug dose, then the AE is treatment-emergent; else,

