- If the start year is the same as the year of the first study drug dose and
 - the start month is missing, then the AE is treatment emergent; else if
 - the start month is present and is the same or after the month of the first study drug dose, then the AE is treatment-emergent; else.
- If the start date is completely missing, then the AE is treatment-emergent.

All other AEs are considered Pre-Treatment Adverse Events (PTAEs).

Patient percentages are based on the total number of treated patients in the particular group including naïve, previously eculizumab-treated patients and total.

Related AEs are defined as possible, probable, or definitely related. Unrelated AEs are defined as unlikely or not related.

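### Neither TEAE definition covers an adverse event that starts before the first dose and worsens or becomes serious on drug; unless the worsening is recorded as a new event, it is counted as pre-treatment

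*Protocol*

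**What the plan says.** Both documents classify an AE by when it started.

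- Protocol 14.9.1: "Treatment-emergent adverse event: Any AE that starts during or after the first infusion of study drug". The serious category is nested in this one: "A treatment-emergent AE (TEAE) that is serious".
- Protocol 11.7 gives the other side of the line: "An AE reported after informed consent but before study drug administration will be considered a pretreatment AE".
- SAP 9.3: "Treatment-emergent AEs (TEAEs) are events with start dates and start times on or after the date and time of the first ALXN1210 dose". After its rules for partial dates it closes the classification: "All other AEs are considered Pre-Treatment Adverse Events (PTAEs".

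Neither definition mentions an increase in grade, or an event becoming serious, after dosing has begun. On how a grade change is recorded, Protocol 11.7.2 says only: "Any change in the severity of an AE should be documented based on specific guidelines in the eCRF Completion Guidelines".

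Pre-treatment AEs (PTAEs) are not discarded. SAP 7.3.2 says: "Analyses of Pre-Treatment Adverse Events (PTAEs) and Treatment-Emergent Adverse Events (TEAEs) will be tabulated and presented separately". It adds: "Listings will be provided for all TEAEs and PTAEs for the Safety Set".

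**The concern.** AE collection begins at consent, and Screening can last 28 days, so an AE record can already be open on Day 1. If that event is mild before dosing and becomes severe or serious afterwards, the part of its course that matters for drug safety happens on drug. An onset-only rule still places it on the pre-treatment side if the record keeps its start date.

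Safety is one of the stated objectives of this single-arm study of about 13 children, and the TEAE tables are where most readers will look for it. Compared with a definition that includes worsening, the onset-only rule can leave such events out of the TEAE counts but can never add any. A PTAE table showing a grade reached on drug would also mislead.

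**Working it through.** The plan states no figure to reproduce. The check is to follow one event through the rules and the planned outputs.

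**1. The event.** An AE starts after consent and before the first infusion, is ongoing at dosing, and then rises in CTCAE grade or becomes serious on drug.

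**2. Classification under each way of recording it.**
- Worsening entered as a new AE with its own start date: the start falls after first dose, so it is a TEAE under both documents.
- Worsening entered on the open record: the start precedes first dose, so it is not a TEAE under Protocol 14.9.1 and is a PTAE under the residual rule in SAP 9.3.

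The choice between the two is left to the eCRF Completion Guidelines, which are not among the documents.

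**3. Where the event appears if it stays on the open record.**

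| Planned output | Place | Limited to TEAEs? | Event shown? |
|---|---|---|---|
| Overall summary, by grade and relatedness | SAP 7.3.2.1 | Yes | No |
| Table by severity | SAP 7.3.2.4 | Yes | No |
| TEAEs leading to treatment discontinuation | Protocol 14.9.1; SAP 7.3.2.1 | Yes | No |
| Treatment-emergent SAE category | Protocol 14.9.1 | Yes | No |
| PTAE tabulation and listing | SAP 7.3.2 | No | Yes |
| SAE by-patient listing | Protocol 14.9.1 | Not stated | Yes, if serious |
| Study withdrawals due to an AE; deaths | SAP 7.3.2.1 | Not stated | Yes, if applicable |
| AE and SAE tables by SOC, PT and relationship | SAP 7.3.2.2, 7.3.2.3 | Not stated | Unclear |

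The last row is unclear because the SAP text there refers simply to AEs and SAEs, while the Safety paragraph of the protocol synopsis describes the corresponding summaries as treatment-emergent.

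**4. Which events are exposed.** The set is narrow:
- Conditions present at entry are recorded as medical history (Protocol 11.1.2, 11.1.3). Under SAP 5.3.1 an exacerbation of a pre-existing condition is itself an AE. With no AE record already open, an on-drug exacerbation has an on-drug start and is a TEAE.
- Exclusion criterion 6 bars active systemic infection in the 14 days before Day 1, so much of the infection scenario cannot enroll. Localized infections and other Screening events remain possible.

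**5. Scale.** One patient's weight in an incidence is 1/n.
- n = 13 (planned enrollment): 1/13 = 7.7 percentage points.
- n = 10 (minimum evaluable): 1/10 = 10.0 points.
- Within the naïve or previously eculizumab-treated group, whose sizes the documents do not give: assuming 8 to 4 patients, 1/8 = 12.5 to 1/4 = 25 points.

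Each figure applies only if the patient has no other TEAE in the same category, because SAP 7.3.2 counts a patient once per category.

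**The case against.** A reader might infer that such an event disappears from the safety tables and that its seriousness is lost. The documents do not support that. PTAEs have their own tables and listings, and Protocol 14.9.1 summarizes and lists SAEs without restricting them to treatment-emergent ones. What is lost is the event's place in the TEAE outputs.

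A reader might also infer that misclassification is automatic. It is not: if the eCRF Completion Guidelines call for a new record when the grade changes, the start-date rule works as it should. This objection stands, and it makes the point conditional. It does not remove the point, because neither document states the convention on which the classification depends.

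A third objection is that the SAP leans the other way elsewhere. Unless the stop date shows that the event ended before dosing, an AE with a wholly missing start date, or a partial one that falls in the dosing year with no month or in the dosing month, counts as treatment-emergent. That is true, so no claim can be made about the net direction of all the AE rules together. But those rules concern uncertain dates and do nothing for an event whose pre-dose start is known. A documented on-drug worsening then gets less protection than an undated event.

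Finally, the anemia case is partly covered by other outputs. Hemoglobin appears in the laboratory shift tables and individual plots (SAP 7.3.3.1), in the stabilized-hemoglobin endpoint, and through anemia as a sign in the breakthrough-hemolysis definition. That stands for anemia, not for AEs in general.

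**Conclusion.** The gap is real and limited. An AE that starts between consent and first dose, is ongoing at dosing, and worsens or becomes serious on drug is counted as a PTAE if the worsening stays on the same record. It is then missing from the TEAE overview, the severity table, the discontinuation count and the treatment-emergent SAE category, though it remains in the PTAE outputs and, if serious, in the SAE listing. The effect on TEAE counts is one-sided relative to a definition with a worsening clause.

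The number of such events is unknown and probably small. The 7.7 points are the weight of one patient, not an estimate of bias, and the study is descriptive, so no test result depends on this. The conclusion rests on one assumption that cannot be checked here: that the eCRF Completion Guidelines do not already require a new record for a worsening.

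**What to change.** Make one of two changes in SAP 9.3:

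- extend the definition so that a TEAE also includes an AE that started before the first dose and increased in CTCAE grade, or became serious, on or after the first dose, tabulated at its post-dose grade; or
- state that such worsening is captured as a new AE record with its own start date, and align the eCRF Completion Guidelines with that.

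The first option needs the date of each grade or seriousness change to be available. The second relies only on the start date already collected, and is simpler if the change dates are not held.

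Protocol 14.1 reserves amendments for changes to the primary or key secondary objectives or to study conduct, so this analysis definition does not need one. Describe and justify it in the CSR. If the first option is taken, also record it in SAP 4.1, which at present reports no departures from the protocol's analyses.

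The cost is one SAP sentence, a short eCRF completion note, and slightly more events in the TEAE tables.

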14.3. Analysis Sets

Efficacy analyses will be performed on the Full Analysis Set (FAS). The FAS will include all patients who received at least 1 dose of ALXN1210 and have at least 1 postbaseline assessment.

Safety analyses will be performed on the Safety Set, defined as all patients who receive at least 1 dose of ALXN1210.

Pharmacokinetic and PD analyses will be performed on all patients who receive at least 1 dose of ALXN1210 and who have evaluable PK and PD data.

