14.9.5. Immunogenicity

Incidence and titers for ADAs to ALXN1210 will be summarized in tabular format.

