4.1. Changes From Analyses Specified in the Protocol

Not applicable

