6.3. Full Analysis (FAS)

The Full analysis set (FAS) will consist of all patients in the Safety Set with a baseline and 1 secondary endpoint measurement post-first ALXN1210 dose.

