7.3.2.1. Overall Summary of Adverse Events

An overall summary table of TEAEs will be presented using summary statistics (n, %). The number of events (n) and number of patients with events (n, %) will be displayed for the following events subcategories:

- Total number of TEAEs and patients with TEAEs
- Related TEAEs
- Not related TEAEs
- Grade 1 TEAEs
- Grade 2 TEAEs
- Grade 3 TEAEs
- Grade 4 TEAEs
- Grade 5 TEAEs

Related AEs are defined as AEs that are possibly, probably, or definitely related to study treatment. Not related AEs are defined as AEs that are unlikely or not related to study treatment.

The number and percentage of patients who withdraw from the study due to an AE, who have any TEAE leading to study treatment discontinuation, or who died on study will be presented. These statistics will be prepared separately for SAEs, with the exception of severity grading.

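### SAP 4.1 declares no changes from the protocol, yet the SAP leaves out two promised safety outputs and narrows the Full Analysis Set

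*Protocol*

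**What the plan says.** **Infusion-time adverse events.** Protocol 14.9.1 names them among the TEAE categories to be tabulated: "TEAEs during study drug administration, severe TEAEs, and SAEs will be summarized". It names them again among the listings: "Detailed by-patient listings of TEAEs, SAEs, related TEAEs, TEAEs during study drug administration". In SAP 7.3.2.1, counts "will be displayed for the following events subcategories", and those are all TEAEs, related, not related, and Grades 1 to 5. Patients who withdraw because of an AE, those "who have any TEAE leading to study treatment discontinuation, or who died on study will be presented", complete the overview. SAP 7.3.2.2 to 7.3.2.5 add tables by SOC and PT, relationship and severity, a listing of deaths, and the meningococcal AESI. No category or listing is defined by the time of infusion.

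**ADA titers.** Protocol 14.9.5: "Incidence and titers for ADAs to ALXN1210 will be summarized in tabular format". SAP 7.3.3.4 plans the number and percentage of patients with ADA and with neutralizing antibodies. SAP 5.3.6 still says that titer is tested.

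**Full Analysis Set.** Protocol 14.3: "The FAS will include all patients who received at least 1 dose of ALXN1210 and have at least 1 postbaseline assessment". SAP 6.3 instead takes Safety Set patients "with a baseline and 1 secondary endpoint measurement post-first ALXN1210 dose". SAP 7.2 puts the secondary efficacy analyses on this set.

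**Declared changes.** SAP 4.1: "Not applicable". SAP 4.2 covers changes from the previous SAP version and explains none of these differences.

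**The concern.** SAP section 4 says that the SAP sets out only the analyses going into the 26-week report. An output it does not name is therefore one that the programming team has no instruction to produce. Infusion reactions are the subject of Protocol Appendix B, and a serious one is a ground for permanent discontinuation in Protocol 8.3.1. Immunogenicity is one of the risks in Protocol 5.1.2. These are outputs that a reader of the report would look for.

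The FAS wording matters because of a rule elsewhere in the SAP. SAP 7.2.2 counts patients who withdraw for lack of efficacy as failures for transfusion avoidance, stabilized hemoglobin and breakthrough hemolysis. That rule operates inside the FAS. A treated patient left out of the FAS never reaches it.

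With SAP 4.1 empty, nothing prompts the study report to describe and justify these differences, as Protocol 14.1 requires for changes in analysis methods.

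**Working it through.** The question is mainly textual, so the two documents are compared item by item. Arithmetic is used only to illustrate the FAS item.

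1. **Infusion-time TEAEs.** The protocol requires a summary and a listing; the SAP has neither. What remains is the general listing of all TEAEs (SAP 7.3.2), the SOC/PT, relationship and grade tables, and a count of interrupted infusions (SAP 7.3.1). The events are still reported, but a reader cannot tell which occurred during an infusion. The output looks derivable: Protocol 9.2 has the actual time of every dose recorded, and SAP 9.3 already uses AE start times.

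2. **ADA titers.** The protocol requires incidence and titers; the SAP tabulates incidence only. The titer data exist under SAP 5.3.6.

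3. **FAS.** Both definitions require a dose. The protocol then asks for any postbaseline assessment. The SAP asks for a baseline and a post-dose secondary endpoint measurement. The extra exclusions are therefore (a) a treated patient with no baseline, and (b) one whose only postbaseline data are of another kind, such as vital signs or PK. The SAP does not say which endpoint must be measured, or whether transfusion records or breakthrough monitoring count.

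4. **How likely is (a) or (b)?** Unlikely.
   - Protocol Table 1 schedules chemistry with LDH, and hematology, at every primary-period visit and at early termination.
   - It has transfusions recorded during and between visits, and breakthrough hemolysis monitored continuously.
   - Screening LDH is an eligibility criterion (Protocol 8.1), and a missing Day 1 value is replaced by Screening (Protocol 14.11.1).

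5. **Size if it happened.** With x responders among n treated patients, dropping one non-responder moves the proportion from x/n to x/(n − 1). The shift is x/[n(n − 1)]. Its maximum is 1/n, reached when everyone else responds (x = n − 1). The counts below are assumed, with exact 95% intervals:
   - n = 12, the enrollment that triggers this report (SAP section 4): 11/12 = 91.7% (61.5 to 99.8) becomes 11/11 = 100% (71.5 to 100). Shift: 1/12 = 8.3 points.
   - n = 13, planned enrollment: 12/13 = 92.3% (64.0 to 99.8) becomes 12/12 = 100% (73.5 to 100). Shift: 7.7 points.
   - n = 10, planned minimum evaluable: 9/10 = 90.0% (55.5 to 99.7) becomes 9/9 = 100% (66.4 to 100). Shift: 10 points.
   - With two non-responders in 12, one of them dropped: 10/12 = 83.3% becomes 10/11 = 90.9%. Shift: 7.6 points.
   - Breakthrough hemolysis mirrors the first case: 1/12 = 8.3% becomes 0/11 = 0%.

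6. **By prior treatment.** SAP 7.2.2 also reports the naïve and previously eculizumab-treated groups separately, and neither document gives their sizes. The 1/n ceiling applies: 12.5 points for an assumed group of 8, 20 points for an assumed group of 5.

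7. **What is unaffected.** AE percentages (SAP 7.3.2) and immunogenicity (SAP 7.3.3.4) use the Safety Set, so the FAS wording does not touch them.

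**The case against.** The best defence is that little would change in practice. With about 13 patients, the all-TEAE listing shows every event, and interrupted infusions are summarized. SAP section 7 opens by saying that all collected data will be documented in tables, figures and listings, which could be read to cover titers. The SAP governs only the 26-week report, and a final report follows. Protocol 14.1 leaves analysis details to the SAP and provides for changes to be described in the study report. The study is descriptive, so no test depends on the FAS.

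Much of this stands, and it limits the point. A reader might infer that the safety data are lost; they are not. A reader might also infer that the SAP's FAS biases the results in the drug's favour. The documents do not support that as an expectation. A patient who withdraws for lack of efficacy with no post-dose LDH, hemoglobin, transfusion or breakthrough record is hard to picture under this schedule. The protocol FAS would itself drop a patient with no postbaseline data at all. Only the increment between the two definitions is at issue, and the figures above show the loss of any one non-responder, not an expected effect of that increment.

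The defence does not make SAP 4.1 accurate. A general promise to document all data does not replace two specific protocol commitments, and the protocol does not confine those commitments to the final report.

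**Conclusion.** The point holds as a minor gap in SAP completeness. Two protocol-specified safety outputs (the infusion-time TEAE summary with its listing, and the ADA titer table) are not planned for the 26-week report. The FAS is worded more narrowly than in the protocol, and SAP 4.1 declares none of this.

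The FAS item is a loose end between SAP 6.3 and SAP 7.2.2, not a demonstrated bias. Its illustrative ceiling is 8.3 points with 12 patients, assuming that exactly one non-responder is excluded and everyone else responds. Group-level effects depend on group sizes that the documents do not give, so a figure such as 20 points is not a finding about this trial.

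**What to change.** - **SAP 7.3.2:** add a summary and a by-patient listing of TEAEs that start during an infusion.
- **SAP 7.3.3.4:** add a table of ADA titers.
- **SAP 6.3:** restore the protocol's FAS wording. Alternatively, state that every treated patient who withdraws for lack of efficacy stays in the denominator for transfusion avoidance, stabilized hemoglobin and breakthrough hemolysis. The first option removes the discrepancy. The second also covers a patient with no postbaseline data, whom the protocol FAS would drop.
- **SAP 4.1:** list and justify any departure that remains. A check against the protocol would also catch smaller ones, such as baseline tables on the FAS only (SAP 7.1.3) where Protocol 14.4 names both the FAS and the Safety Set.

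The cost is SAP wording and a few outputs from data already collected. No new assessments or patients are needed.
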